4.2. SAFETY REVIEW TEAM (SRT)

Instream blinded monitoring will also be performed by the internal GSK Safety Review Team (SRT). Refer the iSRC charter for details.

4.3. INTERIM ANALYSES

A group-unblinded 1st interim analysis on safety and immunogenicity data collected from all participants until 28 days after the first vaccination in Step 2 (Visit 3, Day 29) will be performed by the unblinded biostatistics team at IQVIA (independent data analysis centre [IDAC]). No individual listings will be generated. Results will not impact the continuation of the study itself but will inform further development of the candidate vaccine in other studies.

After unblinding of the Sponsor personnel (partial observer-blind), a 2nd interim analysis on all data up to and including Day 197 (Visit 6) in Step 2 will be performed and individual listings will be generated. At this point, the entire study team will be unblinded.

Document: \\dccar2dnetvnasc01p-lan1.quintiles.net\cp_ops\PROJECTS\Glaxo SmithKline\GSK205480_HAB61752\SAP
Author: PPD Version Number: 1.0
Version Date: 25OCT2022

Template No: CS_TP_BS016 – Revision 7
Effective Date: 01Nov2021

Reference: CS_WI_BS005

All analyses are descriptive and with the aim to characterize the safety and immunogenicity data and therefore no statistical adjustment for interim analyses is required.

Derivations and definitions for the interim analyses will be based on those required for the final analysis contained in this analysis plan, unless deviations are stated within the text.

All tables presenting summary statistics planned for final analysis will be generated at the time of interim analyses, only for the primary cohort (exposed set for safety and per protocol set/full analysis set for immunogenicity analyses). No unblinded individual participant listings and listing tables will be generated at the time of 1st interim analysis. Unblinded individual participant listings and listing tables will be generated for the 2nd interim analysis.

CCI

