9.5.1. Sequence of analyses

A first interim analysis on safety and immunogenicity will be performed by a Sponsor's delegate unblinded statistician on data collected from all participants until 28 days after the first vaccination in Step 2 (Visit 3, Day 29). An interim CSR will be produced but no individual listings will be generated. Results will not impact the continuation of the study itself but will inform further development of the candidate vaccine in other studies. Since some treatment groups of specific participants may be revealed during the interim analysis, the study will be considered single-blind from this point and onwards with the Investigator, site staff and participants remaining blinded up to EoS.

A second interim analysis on safety and immunogenicity may be performed by a Sponsor's delegate unblinded statistician on data collected from all participants until 28 days after the second vaccination in Step 2 (Visit 6, Day 197). No individual listings will be generated.

The final analysis will include all data for at least primary and secondary endpoints up to and including follow-up safety phone contact (Day 337). **CC1**
CC2 A final CSR containing all available data will be written and made available to the investigators.

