10.10.2. Glossary of terms

Adverse event:	Any untoward medical occurrence in a patient or clinical investigation participant, temporally associated with the use of a medicinal product, whether or not considered related to the medicinal product. An AE can therefore be any unfavourable and unintended sign (including an abnormal laboratory finding), symptom, or disease (new or exacerbated) temporally associated with the use of a medicinal product. For marketed medicinal products, this also includes failure to produce expected benefits (i.e., lack of efficacy), abuse or misuse.
Blinding:	A procedure in which 1 or more parties to the trial are kept unaware of the intervention assignment in order to reduce the risk of biased study outcomes. The level of blinding is maintained throughout the conduct of the trial, and only when the data are cleaned to an acceptable level of quality will appropriate personnel be unblinded or when required in case of an SAE. In an observer-blind study, the participant, the site, and Sponsor personnel involved in the clinical evaluation of the participants are blinded while other study personnel may be aware of the treatment assignment. For this study, single-blind means the Sponsor will be aware of the study intervention assignment but the Investigator and/or his staff will not.
Caregiver:	A ‘caregiver’ is someone who 
• lives in the close surroundings of a participant and has a continuous caring role or• has substantial periods of contact with a participant and is engaged in his/her daily health care (e.g., a relative of the participant, a nurse who helps with daily activities in case of residence in a nursing home). In the context of a clinical study, a caregiver could include an individual appointed to oversee and support the participant’s compliance with protocol specified procedures.

Certified copy:	A copy (irrespective of the type of media used) of the original record that has been verified (i.e., by a dated signature or by generation through a validated process) to have the same information, including data that describe the context, content, and structure, as the original.
Combination product	Combination product comprises any combination of 
• drug• device• biological product Each drug, device and biological product included in a combination product is a constituent part.

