1. INTRODUCTION

This document describes the rules and conventions to be used in the presentation and analysis of safety and immunogenicity data at interim and final analyses for Protocol 205480 (H02_01TP). It describes the data to be summarized and analyzed, including specifics of the statistical analyses to be performed. This statistical analysis plan (SAP) is based on final protocol dated 23 August 2022. In scope of this analysis are all primary and secondary objectives and part of CCI [REDACTED]. The iSRC/SRT analyses and the remaining CCI [REDACTED] will be described in separate documents.

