16.1.1. ADVERSE EVENTS LEADING TO DISCONTINUATION FROM STUDY OR FROM TREATMENT

Adverse events leading to permanent discontinuation from study and leading to discontinuation of study vaccine but continued further study procedures (safety or immunogenicity) will be identified by using the variable pertaining to outcome the Adverse Events page of the (e)CRF, and listed, separately. AEs leading to discontinuation from treatment will be listed.

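### SAP v1.0 conflicts with Protocol Amendment 2 on second-interim listings and on the laboratory baseline, and its text leaves two withdrawal-AE endpoints without a count

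*SAP*

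**What the plan says.** SAP v1.0 is dated 25 October 2022 and names its source: "This statistical analysis plan (SAP) is based on final protocol dated 23 August 2022". Its section 3.3 declares no change from the protocol's analyses. The current protocol is Amendment 2, of 21 August 2023. The two texts differ in three places.

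**Second interim.** SAP 4.3 begins "After unblinding of the Sponsor personnel (partial observer-blind), a 2nd interim analysis" and says that the analysis will be performed. It then orders individual listings twice, the second time as "Unblinded individual participant listings and listing tables will be generated for the 2nd interim analysis". Protocol 9.5.1 says "A second interim analysis on safety and immunogenicity may be performed". For each of the two interims in turn, it states that "no individual listings will be generated".

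**AEs leading to withdrawal or withheld vaccination.** Protocol 9.4.1 (primary, Day 1 to Day 197) and 9.4.2 (secondary, withdrawal only, Day 197 to Day 337) require numbers and percentages of participants on the Exposed Set. SAP 16.1.1 plans separate listings and closes with "AEs leading to discontinuation from treatment will be listed".

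**Laboratory baseline for Day 8.** Protocol 9.4.1 uses Day 1, or a screening draw taken no more than 3 days before first vaccination. The Synopsis and Table 3 carry the same footnote. SAP 6.5 allows the screening value whenever the Day 1 value is missing and sets no limit on its age.

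**The concern.** A programmer works from the SAP. Followed as written, section 4.3 produces unblinded participant-level output that the protocol excludes at that point. Section 6.5 builds a laboratory baseline that the protocol excludes. The second matters more for results: SAP 16.2 tabulates haematology and biochemistry against baseline, both by reference range and by grade, and this is the primary laboratory endpoint. Haemoglobin is also graded on its change from baseline.

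For the withdrawal AEs, the SAP text does not say where the protocol's number and percentage would be produced. SAP 4.3 generates at the interims the summary tables planned for the final analysis, and the first interim has no listings. If no table exists, the first interim would show these events only through the reasons in the disposition table.

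**Working it through.** **1. Second interim, side by side**

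| Item | SAP 4.3 | Protocol 9.5.1 |
|---|---|---|
| Is it done? | Will be performed | May be performed |
| Individual listings | Generated, unblinded | None |
| Who is unblinded | Sponsor personnel, then the entire study team | "the study will be considered single-blind from this point and onwards with the Investigator, site staff and participants remaining blinded up to EoS" |

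The first two rows conflict. The third need not. SAP 4.3 speaks of sponsor personnel just before it mentions the study team, so the team is most naturally sponsor-side staff. The protocol glossary allows their unblinding: "single-blind means the Sponsor will be aware of the study intervention assignment but the Investigator and/or his staff will not". The text shows no loss of blinding at the site or among participants. The conflict is about the listings and whether the interim is optional.

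**2. Withdrawal-AE endpoints**

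- Endpoints without a count in the SAP text: 1 of the 6 primary endpoints in protocol 9.4.1, and 1 of the 2 long-term safety endpoints in 9.4.2.
- The nearest tabulation is the disposition table in SAP 9, which gives reasons for early discontinuation. It uses the Enrolled Set (as randomised), not the Exposed Set (as administered), and does not divide reasons at Day 197. Treatment discontinuation is only a listing.
- For comparison, SAP 16.1 does specify a count of participants with SAEs, divided at Day 197. It has no matching sentence for withdrawal AEs.
- Weight of one participant: 1/24 = 4.2%, 1/12 = 8.3%, 1/6 = 16.7%.

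**3. Age of a screening baseline**

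- Screening window (protocol Table 1): Day -21 to Day -1, which is 21 days.
- Accepted by the protocol: Day -3 to Day -1, which is 3 days.
- Accepted by the SAP only: 21 - 3 = 18 days (Day -21 to Day -4), or 18/21 = 85.7% of calendar days. This is not a share of participants.
- Oldest baseline accepted: 3 days under the protocol, 21 days under the SAP.

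**4. What an older baseline can do to a haemoglobin grade**

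Protocol Appendix 9 grades the fall from baseline as Grade 1 up to 1.5 g/dL, Grade 2 above 1.5 to 2.0, and Grade 3 above 2.0 to 5.0. The Grade 2 band is 2.0 - 1.5 = 0.5 g/dL wide. Let *d* be the fall from the Day 1 value that was not obtained, and *δ* the amount by which the screening value exceeds it. The SAP then grades *d + δ*. The values of *δ* below are assumptions, since the documents give none.

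| d | δ | d + δ | Grade |
|---|---|---|---|
| 1.5 | 0 | 1.5 | 1 |
| 1.5 | 0.1 | 1.6 | 2 |
| 1.5 | 0.6 | 2.1 | 3 |

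To skip Grade 2 requires *d* ≤ 1.5 and *d + δ* > 2.0, so *δ* must exceed 0.5 g/dL. Under the protocol's rule the same participant would have no eligible baseline and no change-from-baseline grade.

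**The case against.** The best defence is version lag. The SAP predates both amendments. Amendment 1 revised section 9.5.1 and introduced single-blinding after the first interim, and Amendment 2 added the baseline footnote, so an October 2022 plan could not reflect them. This explains part of the mismatch, though the documents do not show that the amendments caused all three differences. It does not remove the mismatch: v1.0 is the only SAP supplied, and it governs both the interim and final analyses.

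On the listings, all analyses are descriptive, Day 197 is the primary completion date, and the sponsor may know assignments by then. That stands. It limits the consequence but leaves two instructions that cannot both be followed.

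On the withdrawal AEs, SAP 1 puts all primary and secondary objectives in scope, and SAP 8 leaves table content to templates that were not available. Protocol 7.2 has three AE categories among its withdrawal reasons, so disposition may show AE withdrawals from the study by group. Withdrawal after a Grade 3 AE is also a holding rule at one participant. All of this stands. What remains is a gap in the SAP text, not a proven missing analysis. The open items are the analysis set, the Day 197 division and withheld doses.

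On the baseline, SAP 6.5 is silent on age and does not state a different limit. Footnote 6 of protocol Table 1 lets a site skip the Visit 1 sample only after a screening draw in the preceding 3 days, and the SAP fallback fits that case. Everyone else has a scheduled Day 1 draw. So the gap matters only when that draw is missed or fails and the screening sample is older. The number affected should be small, but the rule as written still covers them.

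**Conclusion.** The concern holds. Two SAP rules conflict with the current protocol. One orders individual listings at an interim that the SAP treats as certain and the protocol as optional. The other accepts a laboratory baseline up to 21 days old where the protocol's limit is 3. The third part is a gap in the SAP text for two protocol endpoints, which the templates may close.

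The size is modest. The listings conflict has no shown effect on any estimate. The baseline rule touches a primary safety endpoint, but only for participants with no Day 1 sample and a screening sample taken on Day -21 to Day -4. The documents give no expected number. In groups of 6 to 24, each such participant is 16.7% to 4.2% of the denominator. The conclusion assumes that v1.0 is the SAP in force and reads the study team in SAP 4.3 as sponsor-side staff. The haemoglobin example is illustrative.

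**What to change.** Amend the SAP to match Protocol Amendment 2:

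- **4.3:** remove individual listings at the second interim, describe that interim as optional, and state that the Investigator, site staff and participants stay blinded to end of study.
- **6.5:** accept a screening haematology or biochemistry value as the Day 1 baseline only if drawn within 3 days of first vaccination.
- **16.1.1:** specify, or cross-reference in the templates, the number and percentage by group on the Exposed Set for AEs/SAEs leading to withdrawal or withheld vaccination (Day 1 to Day 197) and to withdrawal (Day 197 to Day 337).
- **1 and 3.3:** cite the current protocol and record any departure that is intended.

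The cost is one SAP amendment, at most one additional table, possibly a few missing laboratory baselines, and no individual listings before the final analysis.

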4.4. FINAL ANALYSIS

Final, planned analysis identified in this SAP will be performed by IQVIA Biostatistics following sponsor authorization of this Statistical Analysis Plan, database lock, and unblinding of treatment.

A final analysis will be performed including all data collected including the extended safety follow-up period up to Day 337 in Step 2.

A final CSR will be produced after Day 337 in Step 2.

5. ANALYSIS SETS

5.1. ENROLLED SET

Participants who provided informed consent and were randomized or received study intervention or underwent a post-screening procedure. The allocation in a group is based on the planned intervention, i.e. 'as randomized'.

Note: participants who never passed screening even if rescreened (screening failures) and participants screened but never enrolled into the study (met eligibility but not needed for the study) are excluded from the Enrolled analysis set.

5.2. EXPOSED SET (ES)

All participants who received at least 1 dose of the study intervention. The allocation in a group is based on the administered intervention.

Document: \\dccar2dnetvnasc01p-lan1.quintiles.net\cp_ops\PROJECTS\Glaxo SmithKline\GSK205480_HAB61752\SAP
Author: PPD Version Number: 1.0
Version Date: 25OCT2022

Template No: CS_TP_BS016 – Revision 7
Effective Date: 01Nov2021

Reference: CS_WI_BS005

5.2.1. UNSOLICITED SAFETY SET

All participants who received at least 1 dose of the study intervention (ES) that report unsolicited adverse events (AEs)/report not having unsolicited AEs. The allocation in a group is based on the administered intervention.

Note: Participants will be considered to have reported no unsolicited AEs if they are enrolled in the study up to 28 days after vaccination without providing AEs.

5.2.2. SOLICITED SAFETY SET

All participants who received at least 1 dose of the study intervention (ES) who have solicited safety data for that intervention. The allocation in a group is based on the administered intervention.

5.3. FULL ANALYSIS SET (FAS)

All participants who received at least 1 dose of the study intervention and have post-dose immunogenicity data. The allocation in a group is based on the randomized intervention. The FAS for immunogenicity will be defined by time point.

The Full Analysis Set will be used as second-line analysis for secondary **CCI** endpoints if the percentage of vaccinated participants (in any study group at any time point) with serological results excluded from the Per-protocol Set for analysis of immunogenicity is 10% or more.

5.4. PER-PROTOCOL SET (PPS)

All eligible participants who received each dose as per-protocol, had immunogenicity results post-dose, complied with dosing/blood draw intervals, without intercurrent conditions that may interfere with immunogenicity, without prohibited concomitant medication/vaccination and without protocol deviation leading to exclusion (Section 11.2). The PPS for immunogenicity will be defined by time point.

The protocol deviations leading to exclusion of the participants are described in Section 11.2. Four Per-protocol Sets for analysis of immunogenicity will be derived:

5.4.1. PER-PROTOCOL SET FOR ANALYSIS OF IMMUNOGENICITY AT DAY 29

The analysis set will contain all participants included in the Per-protocol Set, with no protocol deviations leading to exclusion until Day 29 and with at least 1 valid immunogenicity data available at Day 29.

Document: \\dccar2dnetvnasc01p-lan1.quintiles.net\cp_ops\PROJECTS\Glaxo SmithKline\GSK205480_HAB61752\SAP
Author: **PPD** Version Number: 1.0
Version Date: 25OCT2022

Template No: CS_TP_BS016 – Revision 7
Effective Date: 01Nov2021

Reference: CS_WI_BS005

5.4.2. PER-PROTOCOL SET FOR ANALYSIS OF IMMUNOGENICITY AT DAY 169

The analysis set will contain all participants included in the Per-protocol Set, with at least 1 immunogenicity data available at Day 169 without any protocol deviations that could lead to exclusion.

5.4.3. PER-PROTOCOL SET FOR ANALYSIS OF IMMUNOGENICITY AT DAY 176

The analysis set will contain all participants included in the Per-protocol Set, with at least 1 immunogenicity data available at Day 176 without any protocol deviations that could lead to exclusion.

5.4.4. PER-PROTOCOL SET FOR ANALYSIS OF IMMUNOGENICITY AT DAY 197

The analysis set will contain all participants included in the Per-protocol Set with at least 1 immunogenicity data available at Day 197 without any protocol deviations that could lead to exclusion.

Analysis	Enrolled Set	Exposed Set	Un-solicited Safety Set	Solicited Safety Set	Full Analysis Set*	Per-protocol (PP) Set			
						PP Set Day 29	PP Set Day 169	PP Set Day 176	PP Set Day 197
Participant Disposition	✓								
Baseline Assessments		✓							
Concomitant Medications		✓							
Exposure		✓							
Immunogenicity Analysis					✓	✓	✓	✓	✓
Protocol Deviations		✓							
Solicited Adverse Events				✓					
Unsolicited Adverse Events			✓						
Solicited and Unsolicited Adverse Events		✓							
Other Safety (lab, vitals)		✓							

* Analysis in this set will be performed if the percentage of vaccinated participants with serological results excluded from the Per-protocol Set for analysis of immunogenicity is 10% or more

Document: \\dccar2dnetvnasc01p-lan1.quintiles.net\cp_ops\PROJECTS\Glaxo SmithKline\GSK205480_HAB61752\SAP
 Author: PPD Version Number: 1.0
 Version Date: 25OCT2022

Template No: CS_TP_BS016 – Revision 7
 Effective Date: 01Nov2021

Reference: CS_WI_BS005

6. GENERAL CONSIDERATIONS

The safety summaries, data listings and figures as well as the statistical analysis of the variables will be the responsibility of the study biostatistician at IQVIA.

6.1. SUMMARY STATISTICS

For qualitative variables, the population size (N for sample size and n for available data) and the percentage (of available data) for each class of the variable will be presented. Quantitative variables will be summarized using descriptive statistics, including N (with data available), mean, standard deviation (SD), coefficient of variation (CV%), median, Q1, Q3, minimum, and/or maximum values. Geometric mean will be included for immunogenicity parameters, where applicable. Coefficient of variation will not be presented for change from baseline results.

The exact two-sided 95% CIs for a proportion within a group will be calculated using the Clopper-Pearson exact method.

The geometric mean antibody concentrations (GMCs) and CCI [REDACTED] calculations will be performed by taking the anti-log of the mean of the log10 titer transformations. Confidence interval for geometric means will be derived by raising 10 to the confidence interval associated with mean of log10 values i.e., CI of geometric mean = $10^{(CI \text{ for the mean of log10 values})}$. All participants with valid data will be considered. Participants whose antibody titers are below the cut-off of the assay will be given an arbitrary value of half the cut-off for the purpose of GMC/CCI [REDACTED] calculation.

6.2. TREATMENT SUMMARIZATION

In general, data will be presented for each study group:

Step	Study Groups
1a	Low dose without Alum
	Control
1b	Low dose with Alum
	Control
2	Full Dose without Alum
	Full Dose with Alum
	Control

Document: \\dccar2dnetvnasc01p-lan1.quintiles.net\cp_ops\PROJECTS\Glaxo SmithKline\GSK205480_HAB61752\SAP
Author: PPD [REDACTED] Version Number: 1.0
Version Date: 25OCT2022

Template No: CS_TP_BS016 – Revision 7
Effective Date: 01Nov2021

Reference: CS_WI_BS005

Data for all steps and all study participants combined will also be presented when appropriate (disposition and demographic summaries). Control subjects from Steps 1a, 1b and 2 may be pooled together if needed.

6.3. PRECISION

Safety data (vital signs, laboratory parameters) and immunogenicity data will be reported to the same precision as the source data.

For the reporting of descriptive statistics, the mean, median, Q1, Q3, standard deviation, standard error and confidence intervals will be presented to one digit more precision than the source data. The minimum and maximum will be presented to the same precision as the source data. Coefficient of variation (%) will always be reported to 1 decimal place. P-values, if any, shall be reported to four decimal places or as <0.0001.

The number of decimals used when displaying geometric mean concentrations (GMC)/CCI and their confidence limits is shown in the following table:

GMC/ CCI value	Number of decimals to display
<0.1	3
>=0.1 and <10	2
>=10 and <1000	1
>=1000	0

When multiple categories of CCI/GMC values are present in the same table, the number of decimals displayed should match that of the smallest category (i.e., the one with the higher number of decimals). GMR (geometric mean ratios) or CCI/GMC ratios and their confidence limits will be displayed with 2 decimals regardless of the actual values.

